Cover page

Title: Effectiveness of a home-based peer support program for Chinese mothers with low breastfeeding self-efficacy to increase the exclusivity and duration of breastfeeding: a randomized controlled trial.

NCT number: NCT04621266

Document date: 6th April 2020

Document: Study Protocol

Study Protocol

Title: Effectiveness of a home-based peer support program for Chinese mothers with low breastfeeding self-efficacy to increase the exclusivity and duration of breastfeeding: a randomized controlled trial.

Background Information

The World Health Organization's (WHO) Global Strategy for Infant and Young Child Feeding, which aims to improve rates for breastfeeding recommends that national governments develop a network of community-based mother-to-mother breastfeeding support groups and 'lay and peer counsellors' to enhance existing service [1]. Professional health workers can help improve breastfeeding practices. In resource limited-settings, lack of health workers hinders effective breastfeeding and emotional support. Therefore, we have to depend on peer support to provide knowledge, experience, emotional or practical help. When mothers participate in groups of social activities or receive one-on-one counseling from another mother in the community, they can communicate with each other and exchange knowledge among themselves. Such one on one or group peer support for mothers allow them to support each other, helps in decision making and subsequently empower them [2]. Thus, these interventions have potential to improve breastfeeding practices and child wellbeing [3]. Such interventions have therefore been considered as sustainable alternative to counseling in primary health care settings [4]. These are potentially lower cost interventions compared to those provided by professional health care workers [5]. Recently updated Cochrane review based on 52 RCTs including 37 high income countries indicate that extra support was likely to be more effective in settings with high initiation rates, when delivered face-to-face when offered proactively and on an on-going scheduled basis and tailored to the needs of the population [6].

Peer counselling is being introduced worldwide in supporting mothers' needs for successful maintenance of breastfeeding. Findings from a Cochrane review suggest that postnatal care at home may reduce infant health service utilization in the weeks following the birth, and that more home visits may encourage more women to exclusively breastfeed [7]. In high resource settings healthy women and babies are frequently discharged from hospital within one or two days of birth, potentially home visits in the first few days of the birth by healthcare professions or trained support workers offer opportunities for assessment of the mother and new born, health education, infant feeding support, emotional and practical support.[8-11] By having existing trained peer counsellors (PC) by La Leche League (HK) from our previous project, we propose to conduct a (web-based) home-based peer support programme for mothers who intend to breastfeed but have a low self-efficacy in breastfeeding. We understand mothers are often housebound and find it difficult to attend group support or seek help during the first month postpartum which is the critical period in sustaining exclusive breastfeeding and are at high risk in developing postpartum depression. Peer supporters help women overcome their breastfeeding problems, and women report improved mental health through increased self-esteem, confidence and well-being [12].

In Hong Kong around 20% of women are affected by mental illness either during pregnancy or in the 12 months after giving birth. These include anxiety, depression and postpartum psychosis. Any of these can have a profound effect on breastfeeding and it is important that families can access support at this critical time. There is evidence that breastfeeding can have a preventive effect on mental illness developing. Mothers who plan, but unable to breastfeed their babies are more likely to suffer from postnatal depression. A large scale research study in the UK showed that mothers who planned to breastfeed and who actually went on to breastfeed were around 50% less likely to become depressed than mothers who had not planned to, and who did not, breastfeed. Mothers who planned to breastfeed but who did not go to breastfeed were over twice as likely to become depressed as mothers who had not planned to, and who did not breastfeed [13]. Due to the nature of the study's design, it cannot prove that not breastfeeding raises the risk of postnatal depression. However, it highlights the need to support new mothers who want to breastfeed but are unable to do so. Around 20% of women develop postnatal depression during pregnancy or in the 12 months after giving birth which has long-term sequelae on the family and the infant's psychosocial development.

A Cochrane Review of support for breastfeeding mothers aimed at what kind of support can be provided to help mothers solve any problem concluded that trained volunteers and doctors and nurses had a positive impact on breastfeeding. Factors that may have contributed to the success for women who

exclusively breastfed were face-to-face contact, volunteer support, and specific schedule of four to eight contacts are more likely to succeed with women practicing exclusive breastfeeding [14]. A systematic review indicated that community based peer support for mothers is effective in increasing the duration of exclusive breastfeeding, moreover mothers are more likely to exclusively breastfeed when they receive peer support one on one or through a mother's group [15]. Therefore a feasibility randomized controlled trial (RCT) of home-based breastfeeding peer support programme was conducted by our team to determine if a future definitive RCT could be conducted to improve breastfeeding outcomes among new mothers who intend to breastfeed but have low self-efficacy on breastfeeding. Participants were recruited on a postnatal ward, eighty-five mothers were approached and 20 were screened eligible and randomly allocated into the two arms (with peer support intervention versus usual care). A higher percentage of mothers' exclusively breastfed at 1 month (44% versus 33%), 2 months (43% vs 25%) and 4 months postpartum (50% vs 33%) in the peer support arm compared to usual care. Views on the program from qualitative interviews from the participants after the intervention were positive and met their expectation. The advantages of the intervention stated by all participants were they have a point of contact in which they have someone to speak to directly about their problems. Volunteer's response is quicker and the process is faster compared with 'usual maternity care'. Peer support provided more emotional support and care which relieves pressure for first-time mothers. Participants feel more comfortable to speak with the volunteers compared to health professionals as they found nurses in hospital and clinics were too routine and more concerned with scientific or quantitative issues. These findings from the feasibility study demonstrate that women value peer supporters as mothers with similar experiences who can relate to their own situation through a shared language. Therefore, a home-based peer support intervention is recommended for the proposed study.

Summary of known and potential risks and benefits

As intervention involves peer support (face-to-face) and no invasive procedures will be involved, risks to women and their infants are likely to be minimal. In terms of confidentiality and anonymity, analysis will take place on anonymous data. Personal identifiable data will be held separately from the anonymous data used for analysis.

Benefits include women gaining in awareness of the value of breastfeeding for their own and for their infant's health, and feeling supported in this aspect of caring for their infants.

1 Objectives and Purpose

The aim of the proposed study is to evaluate the effectiveness of a (web-based) home-based breastfeeding peer support program in improving breastfeeding practices among women with low breastfeeding self-efficacy.

2 Design

This is a two armed blinded randomized controlled trial. 442 women will be recruited from four hospitals. Trained peer counsellors will provide home based (web based due to 5th Covid wave) one-to-one breastfeeding intervention sessions to the participants.

Study Procedure

1. Recruitment:

Mother-infant pairs will be recruited from a hospital that has an average of 300+ deliveries per month. Eligible participants will be approached and invited to join the study in antenatal clinics. Women who agree to participate and sign the consent form will be invited to complete the following forms available both in Chinese or English version:

- a. Demographic Data Collection Form
- b. Breastfeeding Self-efficacy and Attitude Data Collection Form

Research assistant will complete the following form from participants' medical records:

- a. Maternal and Birth Data Collection Form

This study includes two study arms:

- a. Home-based peer support programme (web-based) and standard usual care
- b. Control group will be standard usual care

Participants will be randomized following completion of the baseline data. Block randomization procedures with random block sizes of 2, 4 or 6 will be used. An independent research assistant who will not participate in participant recruitment, data collection and analysis will generate the allocation sequence using the statistical software Stata 14. Allocation sequences will be kept in sequential numbered, opaque, sealed envelopes. Outcome assessors will be blinded to the treatment allocation. The research assistant will draw the first sealed envelope from the box and participants will be allocated to that intervention group.

2. Telephone follow-up call:

The participants will receive follow-up telephone calls at one, two, four and 6 months postpartum. Each follow-up call will take approximately 15 minutes.

The following forms will be completed by a research assistant in the telephone follow-ups:

One month follow-up:

- a. One-Month Follow-up Data Collection Form

Two months follow-up:

- a. Two-Month Follow-up Telephone Data Collection Form
- b. Breastfeeding Self-efficacy and Attitude Data Collection Form

Four months follow-up:

- a. Four-Month Follow-up Telephone Data Collection Form
- b. Breastfeeding Self-efficacy and Attitude Data Collection Form

Six month follow-up:

- a. Six-Month Follow-up Telephone Data Collection Form

These data collection forms will be completed if needed:

- b. Weaning Data Collection Form (if participants' babies have been weaned)
- c. Return to Work Data Collection Form (if participants have return to work)

Data Sources

Data collection will consist of: (1) baseline demographic data will include data such as education, income, employment, family composition, antenatal education, (2) maternal and infant data which will include data on the mother's previous obstetrical history, delivery data and basic infant health data.

Study Outcome

Primary outcome: Infant feeding status.

Key Measures

- **Infant Feeding Status:** Patterns of breast milk feeding as assessed at each follow up point will be classified according to existing World Health Organization definitions. Infants will be considered exclusively breastfed if they receive no solids, no non-breast milk, or no water or other liquids (other than vitamins or medications). Non-exclusively breastfed infants supplemented with infant-formula or other milk substitutes can, if required, be further classified as high partial breastfeeding (>80% of feeds are breast milk), medium-partial breastfeeding (20 to 80% of feeds are breast milk), low partial breastfeeding (<20% of feeds are breast milk). Infant feeding patterns will also be categorized according to definitions that include both the type and mode of infant feeding: (1) direct breastfeeding only, (2) expressed breast milk only, (3) direct breastfeeding and expressed breast milk feeding, (4) direct breastfeeding and formula feeding, (5) expressed breast milk feeding and formula feeding, (6) direct breastfeeding, expressed breast milk feeding, and formula feeding, and (7) formula feeding only. We will compare the overall duration of any and exclusive breastfeeding among participants in the (web-based) home-based peer support programme to the control group which received standard postnatal care only.

- **Breastfeeding Self-efficacy:** Maternal breastfeeding self-efficacy will be measured using the Breastfeeding Self-Efficacy Scale Short-Form (BSES-SF) (Chinese and English version). The BSES-SF consists of 14 items measured on a 5-point Likert scale that begin with the phrase “I can always.” On the scale 1 indicates “not at all confident” and 5 indicates “always confident.” Total scale scores range from 14 to 70 with higher scores indicating greater breastfeeding confidence and self-efficacy. We will administer the BSES-SF in baseline period and at 2 and 4 months postpartum. We will compare the scores among intervention and control groups. Permission to use the BSES-SF has been granted by the authors of both the original and Hong Kong Chinese versions.
- **Edinburgh Postnatal Depression scale:** Participant’s postpartum depression symptoms will be measured by EPDS, Chinese version. It is an instrument consisting of 10 simple and easily understood items, with rating on a scale from 0 to 3, yielding a total range of 0 to 30. EPDS was developed by Cox et al (1987) and has been widely used for the assessment of postnatal depressive symptoms, but it is not a diagnostic scale for depression, rather a screening tool for those vulnerable to developing depression. The Chinese version of EPDS has been validated and shown to have high sensitivity in detection of postnatal depression. To evaluate the postpartum depressive symptoms, pre (1 month postpartum) and post (2 months postpartum) EPDS will be compared between the two groups.

3 Selection and Withdrawal of Subjects

Study population

To be eligible for inclusion in the RCT, participants must be (1) 18 years of age or older, (2) primiparous mothers, (3) intention to breastfeed, (4) low breastfeeding self-efficacy score (between 14 and 32), (5) singleton pregnancy, (6) term infant (37-42 weeks gestational), (7) Cantonese speaking, (8) HK resident and (9) mother with no serious medical or obstetrical complications.

Participants will be excluded from the study if they fail to meet these criteria and/or if their baby: (1) is <37 weeks gestation, (2) has an Apgar score <8 at five minutes, (3) has a birthweight <2500 grams, (4) has any severe medical conditions or congenital malformations, (5) is placed in the special care baby unit for more than 48 hours after birth, or (6) is placed in the neonatal intensive care unit at any time after birth.

4 Treatment of Subjects

The team members have successfully trained 60 PCs from our previous project. The training programme comprised of 20 hours of classroom teaching and practical sessions at Queen Elizabeth Hospital and the Maternal Child Health Centres (MCHCs). The training programme was conducted by UNICEF and La Leche League covering topics such as (1) why breastfeeding is important, (2) how to assure good start of breastfeeding, (3) how to help mother breastfeeding (4) communication skills, (5) common breastfeeding problems, (6) diet and hygiene, (7) maternal illness and needs, (8) local support and role of peer counsellors. The peer counsellors were assessed by their trainers after completing the training programme. Those who pass the assessment can then carry out volunteer work using the train the trainer approach with supervision from La Leche League in MCHCs. Additional training workshop will be arranged for the PCs on solving problems of exclusive breastfeeding and correct breastfeeding technique by team leaders.

The intervention will be based on the PC programme previously conducted in our project except it will be home based (web based) peer support programme by trained PCs. In order to ensure the quality and consistency of intervention, additional training tailored to issues that may encounter in (web-based) home-based contacts will be provided to peer counsellors before the study.

The (web-based) home-based PC programme comprises of two schedules of two contacts during first month postpartum, one contact during 2 months postpartum, one contact during 4 months and one contact during 6 months postpartum, when mothers are most likely to experience difficulties with breastfeeding, and thereafter as needed. Both control and intervention groups will receive the same standard antenatal and postpartum care and a breastfeeding information leaflet. The control group will not receive home based PC programme but a breastfeeding information leaflet so the subjects will be blinded to the nature of the interventions.

5 Assessment of Efficacy

This study aims to assess effectiveness of the peer support intervention. The assessment of efficacy of the intervention will be undertaken at 1 month, 2 months, 4 months and 6 months postpartum using the criteria specified in the study outcomes.

6 Assessment of Safety

This research involves a patient support intervention and we do not anticipate any patient safety issues. The person(s) carrying out the intervention will be trained and with experience in supporting breastfeeding women. However, as a precaution, both the delivery of the intervention and participant outcomes will be closely monitored by the PI and the study investigators

7 Statistic

Data Analysis

To compare the baseline characteristics between the two study groups, t-tests will be used for continuous variables and chi square test for categorical variables. Intention to treat analysis will be conducted. The primary outcome analyses will compare the proportions of participants in the two study groups exclusively breastfeeding at 1, 2, 4 and 6 months postpartum using chi square tests. To control for confounding factors, multiple logistic regression models will be used if required to compare breastfeeding rates between groups at the study follow up points. The secondary outcome analyses will use an independent 2-sample t tests to examine the breastfeeding self-efficacy scores and EPDS scores between the two study groups at baseline and at 1 and 3 months postpartum. To control for confounding factors, multiple linear regression models will be used to compare the scores between the groups at 3 months.

Where appropriate, each estimate will be accompanied by a 95% confidence interval and a 5% level of significance will be used in all statistical tests except where specified. The analysis will be performed using the Stata version 14.0 statistical software.

8 Direct Access to Source Data/Documents

Once data are collected, only the PI will have access to named data which will be kept locked in the PIs office in the School of Nursing. Access to the study data will be available for study related monitoring, audit and regulatory inspection by appropriate bodies. It will also be available for IRB review as appropriate.

9 Quality Control and Quality Assurance

As part of the usual review process in the department, data analysis will be reviewed by the study team to ensure it is appropriate, accurate and correctly interpreted.

10 Ethics

The main ethical considerations for this study are to ensure confidentiality to the participants and to ensure that the participants feel free to either participate in the study or to not participate in the study. The following measures will be taken to address these concerns:

- Participation in the study will be completely voluntary and potential participants will be assured that they will not suffer any consequences of lower standards of care for not participating.
- Participants will be also informed that they may withdraw from the study at any time without any repercussions.
- Informed written consent will be obtained from all participants.
- No specific identifiers (such as name, telephone number, or address) will be included in the data used for analysis or be available to the study team other than the PI. Other study information will not be specific enough, either singly or in combination, to uniquely identify an individual.

This study complies with the principles of the 1996 Declaration of Helsinki.

11 Data Handling and Record Keeping

Anonymised data will be analysed within the School of Nursing. All data collection forms will contain a study ID number only. The only data which will be able to link the participant with the study data are the consent form. All signed consent forms will be kept in the PI's office in a locked filing cabinet.

12 Financing and Insurance

This research does not involve any invasive intervention or medical procedure. The only data collected will be biographical and health related data using questionnaires, data collection sheets, or interviews.

13 Publication Policy

Papers approved by the study team will be published in appropriate peer reviewed journals.

References:

1. Borra, C., M. Iacovou, and A. Sevilla, *New Evidence on Breastfeeding and Postpartum Depression: The Importance of Understanding Women's Intentions*. Maternal and Child Health Journal, 2015. **19**(4): p. 897-907.
2. World Health Organization, *Global strategy for infant and young child feeding*. 2003, World Health Organization: Geneva.
3. Younes, L., et al., *The effect of participatory women's groups on infant feeding and child health knowledge, behaviour and outcomes in rural Bangladesh: a controlled before-and-after study*. J Epidemiol Community Health, 2015. **69**(4): p. 374-81.
4. Lewycka, S., et al., *Effect of women's groups and volunteer peer counselling on rates of mortality, morbidity, and health behaviours in mothers and children in rural Malawi (MaiMwana): a factorial, cluster-randomised controlled trial*. Lancet, 2013. **381**(9879): p. 1721-35.

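### The plan names both four hospitals and one; if four recruit, it does not say how allocation runs across them, and leaving hospital out of the randomisation and primary analysis gives up some balance and precision.

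*Combined protocol and SAP*

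**What the plan says.** Section 2 (Design) states that "442 women will be recruited from four hospitals". Under Study Procedure, item 1 (Recruitment), the source is a single site: "Mother-infant pairs will be recruited from a hospital that has an average of 300+ deliveries per month".

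The allocation procedure is in the same Recruitment item. The unit is the woman: "Participants will be randomized following completion of the baseline data". The method is "Block randomization procedures with random block sizes of 2, 4 or 6 will be used", and no stratification factor is named. An independent research assistant "will generate the allocation sequence using the statistical software Stata 14" (singular), while the next sentence has the plural: "Allocation sequences will be kept in sequential numbered, opaque, sealed envelopes". Then: "The research assistant will draw the first sealed envelope from the box and participants will be allocated to that intervention group". No site or central allocation service is mentioned, and the text does not say where the envelopes are kept.

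Section 7 (Data Analysis) compares the proportions "exclusively breastfeeding at 1, 2, 4 and 6 months postpartum using chi square tests". Multiple logistic regression is available if needed to control confounding, but no covariates are listed. Hospital is not mentioned in that section.

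**The concern.** The two statements on sites are both current text and cannot both be true. The procedure reads as if written for one site. If four hospitals recruit, the plan does not tell staff how the next envelope is obtained, whether there is one list or four, or who keeps them. Order of allocation and concealment should be fixed in writing before the first woman is randomised.

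Hospital is also a natural stratification factor. If breastfeeding rates differ between hospitals, a list that ignores hospital leaves the arms unequal within hospitals by chance, and an analysis that ignores hospital leaves explainable variation in the standard error. At stake are a clear, auditable allocation process and a modest amount of precision.

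**Working it through.** **Inputs from the documents.** N = 442 (Design), taken as given because no power, design rates or dropout are stated from which to reproduce it; this point does not depend on how it was derived. Individual randomisation in random blocks of 2, 4 or 6 (Recruitment). Chi-square tests at a 5% level (section 7). Feasibility rates at 1 month of 44% versus 33% (Background).

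**Assumptions.** Four hospitals, 221 women per arm and no losses. Hospital shares and hospital rates are assumed throughout.

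**1. Balance within hospitals.** Simulation of 442 women, 1,500 runs per setting. The measure is the largest arm difference in any of the four hospitals.

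| Hospital shares | One unstratified list: median (95th percentile) | One list per hospital: median (95th percentile) |
|---|---|---|
| Equal | 12 (22) | 1 (2) |
| 40/30/20/10% | 12 (23) | 1 (2) |

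**2. Precision.** Let p be the mean rate over equal-sized hospitals and B the variance of the hospital rates. The variance of a single outcome is p(1−p), of which B lies between hospitals.

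| Quantity | Rates 20, 30, 40, 50% | Rates 30, 35, 40, 45% |
|---|---|---|
| p | 0.35 | 0.375 |
| B | (0.15² + 0.05² + 0.05² + 0.15²)/4 = 0.0125 | (0.075² + 0.025² + 0.025² + 0.075²)/4 = 0.003125 |
| p(1−p) | 0.2275 | 0.2344 |
| Share, B/[p(1−p)] | 5.5% | 1.3% |
| SE ignoring hospital, √(4p(1−p)/442) | 4.54 points | 4.61 points |
| SE within hospital, √(4[p(1−p)−B]/442) | 4.41 points | 4.57 points |
| Equivalent women, 442 × B/[p(1−p)−B] | 442 × 0.0125/0.215 ≈ 26 | 442 × 0.003125/0.23125 ≈ 6 |

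Under the wider spread, the chance difference between arms due to hospital mix has SD √(4 × 0.0125/442) = 1.06 points. This is a component of the ordinary standard error, not an addition to it: √(4.41² + 1.06²) = 4.54.

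**3. Behaviour of the tests.** Simulation, 3,000 runs per scenario, equal expected hospital shares, mean control rate 33%, effect 0 or 11 points (44% minus 33%). The chi-square test is compared with a Cochran-Mantel-Haenszel (CMH) test stratified by hospital.

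| Control rates by hospital | List | Type I error: chi-square / CMH | Power: chi-square / CMH |
|---|---|---|---|
| All 33% | one | 0.047 / 0.047 | 0.65 / 0.65 |
| 23, 28, 38, 43% | one | 0.043 / 0.044 | 0.65 / 0.66 |
| 13, 23, 43, 53% | one | 0.054 / 0.048 | 0.65 / 0.70 |
| 13, 23, 43, 53% | per hospital | 0.038 / 0.052 | 0.67 / 0.71 |

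The simulation error on a rate of 0.05 is √(0.05 × 0.95/3000) = 0.004, so the one-list results are consistent with 5%. The last row shows why the two changes belong together: with per-hospital lists and large hospital differences, the unadjusted chi-square becomes conservative.

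**The case against.** A reader might infer that the allocation procedure cannot work across four hospitals. The documents do not support that. Allocation follows baseline data collection and the peer contacts are postpartum (section 4), so one assistant holding a central box could allocate for all sites. The plural in "Allocation sequences will be kept in sequential numbered, opaque, sealed envelopes" also leaves one numbered set per hospital open. What stands is that the procedure is unspecified for four sites.

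Nor would dividing one list necessarily destroy the blocking. If consecutive envelopes went to each hospital, only the blocks at the cuts would be broken. With blocks of at most 6, each cut leaves an imbalance of at most 3, so at most 6 per hospital. The documents describe no split, so a breach of concealment is something to guard against in writing, not something they show.

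A reader might also assume that usual care or breastfeeding rates differ between the hospitals. The documents do not say so. Section 4 says only that both arms receive the same standard care, which compares arms and not sites.

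Finally, stratifying by site in an individually randomised trial is a matter of efficiency. Omitting it leaves the test valid, and the gain shrinks to about 6 women under the narrower spread. That stands and limits the size of this point. The optional logistic regression answers it only in part, because neither its trigger nor its covariates are defined.

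**Conclusion.** The contradiction on the number of hospitals is certain and needs correcting. If four recruit, the plan lacks a site-level allocation procedure and makes no use of hospital in the randomisation or the primary analysis.

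It would be wrong to conclude that the treatment comparison is biased or the primary test invalid: simulated type I error for the chi-square test with one list was 0.043 to 0.054. The loss is one of balance (a typical worst within-hospital difference of 12 women rather than 1) and of precision (about 26 women under an assumed 20–50% spread, about 6 under 30–45%). Power for an 11-point effect changes by about 1 point under moderate assumed differences and about 5 points under strong ones. All these sizes rest on assumed hospital rates and shares. If only one hospital recruits, the stratification and adjustment parts fall away.

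**What to change.** Reconcile the Design and Recruitment text on the number of hospitals. If there is one, only the Design text needs correcting.

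If there are four:

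- Generate a separate concealed random-block list and numbered envelope set for each hospital, and state who holds them.
- Record hospital as a baseline variable.
- Make the primary comparison at each time point a CMH test stratified by hospital, with a Mantel-Haenszel risk difference and 95% confidence interval. Keep the unadjusted chi-square as supportive. Name this one estimate as primary: a logistic model with hospital terms gives a conditional odds ratio, which is a different quantity and not interchangeable with the risk difference.
- If randomisation has already begun from one list, still stratify the analysis by hospital.

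The cost is four short lists and envelope sets instead of one, a few sentences of text, and a slightly longer analysis. The sample size stays at 442.

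### The EPDS score labelled 'pre' is taken at 1 month, after randomisation and the first-month peer contacts: it is an outcome and must not serve as a baseline

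*Combined protocol and SAP*

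**What the plan says.** - **EPDS comparison.** Under Key Measures, in the Edinburgh Postnatal Depression scale entry: "pre (1 month postpartum) and post (2 months postpartum) EPDS will be compared between the two groups". The entry does not say whether this means two separate comparisons, a change score or an adjusted comparison.
- **Randomisation.** Under Study Procedure, Recruitment: "Eligible participants will be approached and invited to join the study in antenatal clinics" and "Participants will be randomized following completion of the baseline data".
- **Baseline forms.** The same section lists a demographic form, the "Breastfeeding Self-efficacy and Attitude Data Collection Form" and a maternal and birth form filled in from records. None is named as an EPDS form.
- **Peer contacts.** Section 4 describes "two schedules of two contacts during first month postpartum, one contact during 2 months postpartum", then "one contact during 4 months and one contact during 6 months postpartum", "and thereafter as needed" being added at the end of that sentence.
- **Rationale.** Background Information speaks of "the first month postpartum which is the critical period in sustaining exclusive breastfeeding and are at high risk in developing postpartum depression".
- **Follow-up calls.** These are at 1, 2, 4 and 6 months. There is no 3-month call.
- **Analysis.** Section 7 is the only place that names a test. It plans two-sample t tests of self-efficacy and EPDS scores between arms at baseline, 1 month and 3 months, and a linear regression at 3 months whose covariates are not listed. It mentions no change score.

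**The concern.** A pre/post comparison normally treats the first value as the state before treatment. Here the first value comes after a month in which one arm was offered the programme and the other was not. The Background singles out that same month as the time of high depression risk, so an early benefit is something that the programme might well be expected to produce. The label classes any such benefit as a starting value.

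An analyst who takes the label at its word could subtract the 1-month score, adjust for it, or read an arm difference at 1 month as baseline imbalance. Each choice would hide some or all of an early effect. If the controls caught up during month 2, a change score would make a helpful programme look harmful.

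**Working it through.** **Step 1. Is the 1-month score before or after treatment?** Peer contacts go only to the intervention arm, so allocation must precede the first contact. Section 4 places a block of contacts in the first month. The 1-month EPDS therefore follows allocation and comes at or near the end of that block. This holds whatever the exact day of randomisation.

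**Step 2. Count the scheduled contacts.** The first-month wording can be read as two contacts or as two sets of two, which makes four. The text needs clarifying; both counts are carried here.

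| Reading | By 1 month | Between 1 and 2 months | By 2 months | Share falling between the two scores |
|---|---|---|---|---|
| Two contacts | 2 | 1 | 3 | 1/3 |
| Four contacts | 4 | 1 | 5 | 1/5 |

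The day of the 2-month contact relative to the 2-month call is not stated. The count assumes that the contact comes first.

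**Step 3. What each analysis estimates.** Let d1 and d2 be the benefit (difference between arms, in SD units) at 1 and 2 months, and r the within-arm correlation of the two scores, with equal SDs.

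- Separate comparisons estimate d1 and d2. Nothing is removed.
- A change score estimates d2 − d1. All of d1 is removed. If d1 = d2, the result is 0; if d2 is smaller than d1, the sign reverses.
- Adjusting for the 1-month score estimates about d2 − r × d1. Part of d1 is removed.

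**Step 4. Size, as an illustration only.** The plan gives no EPDS effect size, SD, correlation or power, so it has no figure of its own to reproduce for this outcome. From the plan: 442 women and a 5% significance level. Assumed: 1:1 allocation (442/2 = 221 per arm), two-sided tests, no dropout, d2 = 0.3, r = 0.5 to 0.7, and an effect that builds up equally with each scheduled contact.

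- Direct 2-month comparison: z = 0.3 × √(221/2) = 3.15, power about 88%.
- Change score: z = (d2 − d1)/√(2(1 − r)) × √(221/2).
  - Two contacts by 1 month: d1 = 0.3 × 2/3 = 0.20 and d2 − d1 = 0.10. z = 1.05 (r = 0.5) to 1.36 (r = 0.7), power about 18% to 27%.
  - Four contacts by 1 month: d1 = 0.3 × 4/5 = 0.24 and d2 − d1 = 0.06. z = 0.63 to 0.81, power about 10% to 13%.
- Adjustment for the 1-month score: z = (d2 − r × d1)/√(1 − r²) × √(221/2).
  - Two contacts: 0.20 SD (r = 0.5) or 0.16 SD (r = 0.7), power about 68% or 65%.
  - Four contacts: 0.18 SD or 0.13 SD, power about 59% or 49%.

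**Step 5. Set the EPDS time points side by side.**

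| Place | EPDS time points |
|---|---|
| Recruitment, baseline forms | EPDS not named |
| Telephone follow-up call, forms | EPDS not named; calls at 1, 2, 4 and 6 months |
| Key Measures | 1 and 2 months |
| Section 7 | Baseline, 1 and 3 months |

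Only the 1-month point is common to Key Measures and section 7. For the EPDS, section 7 cannot be carried out as written: its 3-month point has no call and its baseline point has no listed measurement.

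**The case against.** The strongest reply is that nothing in the documents plans to subtract the 1-month score. Key Measures can be read as two scores, each compared between arms. Section 7 names t tests between arms, one of them at 1 month, and that test would capture an early effect in full. Section 5 also lists 1 month as an efficacy assessment point. The section 7 regression does not name the 1-month EPDS among its covariates.

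This stands, and it limits the point. A reader might infer that the planned comparison subtracts the early effect, or that the EPDS outcome cannot show whether peer support reduces depressive symptoms. The documents support neither statement: both hold only if the 1-month score is used as a baseline, which is neither planned nor excluded.

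A reader might also infer that the 1-to-2-month change measures little more than one contact. That goes too far as well. A delayed effect of first-month contacts would also appear in the change. Additional contacts are allowed, although the text does not say whether they can fall before 6 months.

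It is also fair to say that the form lists do not settle whether a baseline EPDS exists. They do not name the EPDS at 1 or 2 months either, and the contents of the forms are not shown.

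What the reply does not do is remove the problem. Section 7 contradicts Key Measures on time points and leaves its covariates open. An analyst who has to reconcile the two could still take 'pre' as the starting value.

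**Conclusion.** The 1-month EPDS is a post-randomisation outcome under a wrong label, on either reading of the contact schedule. The pre/post comparison is undefined, and the one section that names a test conflicts with it. The harm is conditional. A change score would remove the whole effect reached by 1 month, adjustment would remove part of it, and separate between-arm tests would remove none.

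The contrast between about 88% power and about 10% to 27% describes the change-score reading under the assumed inputs; it does not describe the tests named in section 7. The EPDS is a secondary outcome and the primary feeding analysis is untouched. This should be fixed before any unblinded analysis, but it does not threaten the trial.

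**What to change.** 1. In Key Measures, drop the words 'pre' and 'post'. Name the 1-month and 2-month EPDS as two outcomes, each compared directly between arms, with no change score from 1 month and no adjustment for the 1-month value. Randomisation protects both comparisons without a baseline EPDS.
2. In section 7, list the regression covariates and restrict them to variables measured before randomisation.
3. Reconcile the EPDS time points in Recruitment, Telephone follow-up call, Key Measures and section 7, and name the form that carries the EPDS at each point. Correcting the 3-month entry alone would leave the 'pre' label in place.
4. Optionally, give the 10-item EPDS with the baseline forms before randomisation and use it as the covariate.

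Items 1 to 3 change wording only. Item 4 costs one more short questionnaire at enrolment and can be collected only from women not yet randomised.
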